4.5 Patient Assessment

Identification and workup of patients prior to potential enrollment in the study will follow standard-of-care procedures per the treating physician (hepatobiliary surgery, radiation oncology, etc.). If a patient is determined to be eligible for the study, the research coordinator in this study will be asked to come to the clinic to discuss potential enrollment.

4.6 Imaging Information

4.6.1 [⁶⁸Ga]DOTATATE PET Preparation and Injection

The injected dose will be an intravenous weight-based dose of 2 MBq/kg (0.054 mCi/kg) up to a dose of 200 MBq (5.4 mCi). The patient will be instructed to undergo standard patient preparation prior to DOTATATE PET/CT or PET/MRI. PET imaging will begin approximately 60 minutes following injection.

4.6.2 [⁶⁸Ga]DOTATATE PET/MRI Protocol

Whole body imaging

Positron Emission Tomography Acquisition: The patient will be placed on the PET/MRI scanner in the supine position. Initial localizer images will be obtained. Subsequently, static whole body images will be acquired from pelvis to skull base utilizing approximately eight 14 cm detector beds for 3-5 minute acquisitions per bed position. Correction for randoms, scatter, attenuation and reconstructions will be performed per the manufacturer's recommendations.

Whole Body and Liver MRI: Sequences performed will include MR attenuation correction (MRAC), axial and coronal T2 single shot fast spin echo and whole body Dixon-derived sequences.

Following whole body PET imaging, a routine MRI of the liver will be performed at UAB in the PET/MRI scanner per institutional protocol with and without the use of gadoteridol (Prohance) intravenous contrast via a weight-based dose of 0.2 ml/kg. An additional static abdominal PET acquisition will be performed concurrently.

The study protocol has been submitted to, reviewed, and approved by the UAB Radiation Safety Committee (OH&S Project 18-154).

The entire study is expected to take 60-90 minutes to acquire, with the whole body portion taking approximately 30 minutes and dedicated liver portion taking approximately 30 minutes.

4.6.3 [⁶⁸Gal]DOTATATE PET/CT Protocol

If the patient is unable to complete the PET/MRI scan or the patient is felt to be a suboptimal candidate for PET/MRI (due to large volume ascites, surgical clip artifacts, etc.), the patient will undergo whole body PET/CT.

Whole body imaging

Positron Emission Tomography Acquisition: The patient will be placed on the PET/CT scanner in the supine position. Initial localizer images will be obtained. Subsequently, static whole body CT images will be acquired from pelvis to skull base utilizing approximately eight 14 cm detector beds for 3-5 minute acquisitions per bed position. Correction for randoms, scatter, attenuation and reconstructions will be performed per the manufacturer's recommendations.

Whole Body CT: Patient will undergo a noncontrast non-optimized CT for anatomic localization of PET findings per institutional protocol (kVp 140, mA 400). The estimated dose of the CT exam is approximately 6 mSv, equal to approximately two years of background radiation.

The study protocol has been submitted to, reviewed, and approved by the UAB Radiation Safety Committee.

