3.3 Inclusion Criteria

- Known diagnosis of hepatocellular carcinoma, either by imaging criteria or pathology on biopsy
- Standard of care liver MRI or CT demonstrating viable HCC based on arterial contrast enhancement measuring at least 1.5 cm in largest axial dimension

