5.0 Study Parameters

5.1 Primary Endpoint

- Percentage of patients with moderate to high binding of [⁶⁸Ga]DOTATATE on PET examination
- Concordance between [⁶⁸Ga]DOTATATE PET results and liver MRI results

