6.4 Statistical Analysis Plan

This study will largely be exploratory and descriptive. For all clinical and histological evaluations as well as imaging parameters, we will generate summary tabulations of the number of observations, mean, standard deviation, median, minimum, and maximum for continuous variables, and the frequency and percentage for categorical variables. Analyses will be primarily descriptive and graphical in nature. The count, and percentage of patients with HCCs showing activity in their HCC greater than liver and/or spleen will be estimated using Clopper-Pearson (exact) method along with two-sided 95% CI. The estimation will be provided for all 30 patients first, and then by treatment-naïve or not.

Concordance between [⁶⁸Ga]DOTATATE PET results and liver MRI results for patients with SSTR-positive HCC and positive [⁶⁸Ga]DOTATATE PET, intrahepatic and extrahepatic disease will be assessed on MRI/CT alone first, with confidence in interpretation rated on a 1-5 scale (1 = negative, 5 definite). Following this, fused PET/CT or PET/MRI images will be assessed and rated on the same 1-5 scale. Scale 3-4

is defined as positive. The agreement (concordance) between nominal (e.g. scale 1-5) or binary outcome (positive or negative) of [⁶⁸Ga]DOTATATE PET results and liver MRI results will be assessed using Cohen's kappa coefficients with one-side 95% confidence intervals. Based on values of Cohen's kappa, the agreement will be considered as poor (>0.2), fair (0.21-0.40), moderate (0.41-0.60), good (0.61-0.80), and very good (0.81-1.0) ([Dtsch Arztbl Int. Concordance Analysis. 2011 Jul; 108\(30\): 515-521. PMID: 21904584](#)). Bland-Altman diagrams will be used to evaluate agreement for other continuous imaging variables between these two methods. All statistical analysis will be carried on SAS v9.4.

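### For patients scanned by PET/CT, the plan does not say which anatomic scan stands in for liver MRI in the concordance endpoint, and as written the read most naturally falls on a noncontrast localization CT

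*Combined protocol and SAP*

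**What the plan says.** - **Endpoint.** Section 5.1 has two entries under the primary endpoint. The second is concordance between "DOTATATE PET results and liver MRI results". Section 6.4 assesses it with Cohen's kappa and again names liver MRI as the other method.
- **PET/MRI pathway (4.6.2).** "Following whole body PET imaging, a routine MRI of the liver will be performed at UAB in the PET/MRI scanner", with and without gadolinium contrast.
- **PET/CT pathway (4.6.3).** The trigger is: "If the patient is unable to complete the PET/MRI scan or the patient is felt to be a suboptimal candidate for PET/MRI". Ascites and surgical clips are given as examples, and section 3.1 adds claustrophobia. No liver MRI is scheduled here. The anatomic part is described as follows: "Patient will undergo a noncontrast non-optimized CT for anatomic localization of PET findings per institutional protocol".
- **Reads (4.6.4 and 6.4).** In patients with SSTR-positive HCC and a positive PET, "intrahepatic and extrahepatic disease will be assessed on MRI/CT alone first", on a 1-5 confidence scale. The fused PET/CT or PET/MRI images are then rated on the same scale.
- **Analysis set (6.3).** Everyone scanned by either modality.
- **Entry imaging.** Section 3.3 requires "Standard of care liver MRI or CT demonstrating viable HCC based on arterial contrast enhancement". Section 3.1 places the study scan within 4 weeks of the latest conventional CT or MRI. Section 3.4 excludes patients who had locoregional or new systemic therapy between the qualifying scan and the PET.

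**The concern.** The endpoint and the kappa refer to liver MRI, the reads refer to MRI or CT, and one of the two imaging pathways produces no liver MRI. Because section 3.3 accepts CT in place of MRI at entry, a PET/CT patient may have no liver MRI of any kind.

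If the noncontrast CT is scored as the anatomic-alone read and pooled with the MRI reads, the kappa mixes two things: real disagreement between PET and liver MRI, and failure of a noncontrast scan to show the lesion. The protocol recognizes the difference between the instruments. It identifies viable HCC at entry by arterial enhancement, which a noncontrast scan cannot display, and section 3.1 prefers PET/MRI because it characterizes the liver better than noncontrast CT. If the choice is instead left open, two readers could follow the protocol and score different scans, or the choice could be made after the PET result is known.

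**Working it through.** **Which scan would be read.** Sections 4.6.4 and 6.4 do not say whether the CT in the anatomic-alone read is the entry scan or the CT part of the study scan. Three features point to the study scan:
- Section 4.6.4 loads only the PET/CT and PET/MRI images into the reading software and does not mention entry scans.
- The sequence is anatomic images alone, then the fused version, which reads as two views of one examination.
- Section 3.1 justifies the 4-week window by avoiding an effect on clinical management, not by supplying a comparator.

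This is the natural reading, but it is not an explicit instruction. The documents are also silent on a patient who starts PET/MRI, moves to PET/CT, and has part of a liver MRI.

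**The plan's own precision figures.** Section 6.2 gives exact 95% intervals at 20% positivity. Clopper-Pearson limits for 6/30 are 7.71% to 38.57% (stated 7.7% to 38.6%), and for 3/15 they are 4.33% to 48.09% (stated 4.3% to 48.1%). Both reproduce. They concern the positivity endpoint. The plan gives no precision figure for concordance.

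**Inputs.** N = 30 and 20% positivity (section 6.2) give 30 × 0.20 = 6 expected positives. Concordance is restricted to PET-positive patients (section 6.4). The PET/CT fraction is not in the documents, so I assume 10% to 30%, which is 3 to 9 of 30 patients. I also assume that modality is unrelated to positivity.

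**Expected number affected** = 6 × PET/CT fraction:
- 10%: 6 × 0.10 = 0.6
- 20%: 6 × 0.20 = 1.2
- 30%: 6 × 0.30 = 1.8

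**Chance that at least one of exactly 6 positives lacks a study liver MRI** = 1 − C(30 − k, 6)/C(30, 6), with k patients scanned by PET/CT:
- k = 3: 1 − 0.499 = 50%
- k = 6: 1 − 0.227 = 77%
- k = 9: 1 − 0.091 = 91%

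**Weight of one patient.** 1/6 = 16.7 percentage points of raw agreement for each positive whose lesion is missed only because the CT is noncontrast. I use raw agreement because kappa also depends on marginal splits that the documents do not give.

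**Size of a kappa set limited to study liver MRI.** Expected positives fall from 6.0 to 30 × 0.90 × 0.20 = 5.4 with 3 PET/CT patients, and to 30 × 0.70 × 0.20 = 4.2 with 9. Counting standard-of-care liver MRI as well would recover some of these.

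**The case against.** The strongest reply is that every patient already has a usable anatomic scan. Sections 3.3, 3.1 and 3.4 together require an arterial-contrast liver MRI or CT, normally recent, with no intervening locoregional or new systemic treatment. For some PET/CT patients that scan is itself a liver MRI. This stands. A reader might infer that PET/CT patients have no valid comparator; the documents do not support that. The comparator exists but is not named.

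Other parts of the reply also stand:
- A reader might count all 3 to 9 assumed PET/CT patients as affected. Section 6.4 restricts concordance to PET-positive patients, so section 6.3 does not bring in the rest.
- A reader might infer that the loss falls mainly on the previously treated group, since ascites and clips could be commoner there. The documents give no frequency of either by group and state no link between claustrophobia and prior treatment.
- A reader might say that a noncontrast read breaks the scoring rule. Arterial enhancement is an entry criterion. Neither 4.6.4 nor 6.4 makes it the basis of the 1-5 rating, which also covers extrahepatic disease. The noncontrast read is weaker, but no stated rule forbids it.
- The study is a descriptive pilot without a hypothesis test.

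One part does not stand. The reference to MRI or CT in the read does not settle the matter, because the kappa sentence and section 5.1 still say liver MRI, and no rule covers a patient without one.

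**Conclusion.** The point holds in limited form. For PET/CT patients the comparator in a listed primary endpoint is not designated, and the text as written most naturally leads to a noncontrast localization CT being pooled into a kappa labelled as PET against liver MRI.

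The expected number affected is small, about 0.6 to 1.8 of 6 positives. It rests on the assumed 10-30% PET/CT use, the plan's 20% positivity, and independence of modality and positivity. Each case carries much weight, about 17 points of raw agreement, if the lesion is visible with contrast and missed without it. On the same assumptions, the chance that at least one positive lacks a study liver MRI is 50% to 91%.

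Severity is moderate. Under sections 6.1 and 6.2 the step to a therapeutic trial depends on whether 20% or more are PET-positive. Section 4.6.4 judges that against adjacent liver and spleen on PET, so liver MRI does not enter it.

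**What to change.** Amend sections 4.6.4 and 6.4 before any reads begin, so that the comparator is not chosen with PET results in view:

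1. Compute the PET-versus-liver-MRI kappa only in patients who have a liver MRI, whether research or standard-of-care. State whether a partial liver MRI from an uncompleted PET/MRI counts.
2. For PET/CT patients, make the anatomic-alone rating on the contrast-enhanced standard-of-care MRI or CT that qualified them under section 3.3, and load it into the reading software. Keep the noncontrast CT for localization and attenuation correction. View the same contrast scan alongside the fused PET/CT at the second read. Otherwise the anatomic source changes between the two reads, and their difference no longer isolates what PET adds.
3. Report patients whose only contrast scan is CT separately, outside the liver-MRI kappa.

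The cost is protocol wording and the import of scans that already exist; no new scan or reader is needed. There are two downsides. In PET/CT patients the comparator may be up to 4 weeks older than the PET. The kappa set is also slightly smaller: on the assumptions above, 5.4 to 4.2 expected positives instead of 6.0 if only study MRI is counted, and more where a standard-of-care liver MRI exists.

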4.6.4 PET/CT and PET/MRI Imaging Interpretation and Storage

Images from the PET/CT and PET/MRI will be anonymized and subsequently stored and reviewed using a commercially available software package (MIM Encore, Cleveland, OH). The PET and whole body MRI studies will not be available in the UAB PACS system. This is in an effort to blind the treating physicians from making clinical decisions on an experimental imaging technique. The liver MRI images will be sent to clinical PACS and the medical record as part

of standard-of-care imaging and can be used in the clinical-decision making process. No formal interpretation will be generated for the [⁶⁸Ga]DOTATATE-PET or whole body MRI portion of the study.

PET/CT and PET/MRI images will be interpreted by board certified physicians specialized in molecular imaging and abdominal imaging. Images will initially be interpreted as positive or negative for SSTR-positive HCC. HCC lesions will be considered SSTR positive for the purposes of this study if they have higher [⁶⁸Ga]DOTATATE activity than adjacent liver not involved by HCC. The amount of [⁶⁸Ga]DOTATATE binding for intrahepatic HCCs will be further characterized based on visual analysis as less than skeletal muscle (no binding), higher than skeletal muscle but less than or equal to adjacent liver (low binding), higher than adjacent liver but less than spleen (moderate binding) or equal to or greater than spleen (high binding). For patients with SSTR-positive HCC and positive [⁶⁸Ga]DOTATATE PET, intrahepatic and extrahepatic disease will be assessed on MRI/CT alone first, with confidence in interpretation rated on a 1-5 scale (1 = negative, 5 definite). Following this, fused PET/CT or PET/MRI images will be assessed and rated on the same 1-5 scale.

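### The MRI/CT-alone rating follows, and depends on, a positive PET read with no masking of the anatomic reader, so the concordance endpoint is open to review bias

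*Combined protocol and SAP*

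**What the plan says.** Section 4.6.4 describes the reads in this order.

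- The opening step is a PET call: "Images will initially be interpreted as positive or negative for SSTR-positive HCC". Lesions count as positive "if they have higher [⁶⁸Ga]DOTATATE activity than adjacent liver not involved by HCC", and binding in intrahepatic lesions is then graded visually against muscle, liver and spleen.
- For patients with a positive result, the plan continues that "intrahepatic and extrahepatic disease will be assessed on MRI/CT alone first, with confidence in interpretation rated on a 1-5 scale".
- The fused read comes last. Section 6.4 repeats the sequence for the concordance analysis: "Following this, fused PET/CT or PET/MRI images will be assessed and rated on the same 1-5 scale".

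On who reads, section 4.6.4 says only that "PET/CT and PET/MRI images will be interpreted by board certified physicians specialized in molecular imaging and abdominal imaging". The one statement about blinding concerns the decision to keep the PET and whole-body MRI out of the clinical image archive: "This is in an effort to blind the treating physicians from making clinical decisions on an experimental imaging technique".

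Section 5.1 has two bullets under Primary Endpoint. The second is "Concordance between [⁶⁸Ga]DOTATATE PET results and liver MRI results". Section 6.4 assesses it with Cohen's kappa and one-sided 95% confidence intervals.

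**The concern.** A rating made on MRI/CT alone before the fused read is useful because it shows what the anatomic images convey without PET. In this plan the rating is given only to patients whose PET has already been read and called positive. Nothing in the plan separates the readers, hides the PET result from the anatomic reader, imposes a washout, locks the anatomic score or mixes in PET-negative cases.

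The anatomic score may therefore carry information from PET. If it does, agreement between the two ratings partly reflects one rating influencing the other, and the comparison of MRI/CT with fused images no longer shows cleanly what PET adds. The result at stake is the second item under Primary Endpoint.

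**Working it through.** **1. Reading order.** The PET call compares lesion activity with uninvolved liver, so it cannot be made without opening the PET. That call decides who receives the anatomic rating: "For patients with SSTR-positive HCC and positive [⁶⁸Ga]DOTATATE PET, intrahepatic and extrahepatic disease will be assessed on MRI/CT alone first". The rating therefore cannot precede the PET call. The word *first* is relative to the fused read that follows it.

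**2. What the anatomic rater can know.** Two levels follow from the text.

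- Patient level: a rater who knows the protocol knows that each case presented is PET-positive, even if someone else read the PET.
- Site level: if the same reader does both steps, that reader also knows where the activity was. The documents do not say whether this is so.

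**3. The plan's own figures.** Section 6.2 gives exact intervals at 20% positivity. Clopper-Pearson limits are 7.71% to 38.57% for 6/30 and 4.33% to 48.09% for 3/15, matching the stated 7.7% to 38.6% and 4.3% to 48.1%. These concern positivity only. The plan gives no expected agreement or precision for concordance, so there is no concordance figure to reproduce.

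**4. Direction of bias (illustration; all inputs assumed).** Let q be the share of sites positive on PET, s and c the sensitivity and specificity of a masked MRI/CT read against PET, and f the fraction of calls altered by knowledge of PET.

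- Site-level knowledge, a fraction f of discordant calls moved to match PET: a = q[s + (1−s)f] for both positive, and d = (1−q)[c + (1−c)f] for both negative.
- Patient-level knowledge only, a fraction f of all negative sites turned positive: a as above, and d = (1−q)c(1−f).
- In both: b = q − a (PET positive only), e = (1−q) − d (MRI/CT positive only), p_o = a + d, p_e = q(a+e) + (1−q)(b+d), and kappa = (p_o − p_e)/(1 − p_e).

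Take q = 0.5, s = 0.7, c = 0.8. With f = 0, a = 0.35 and d = 0.40, so p_o = 0.75, p_e = 0.50 and kappa = 0.25/0.50 = 0.50. With f = 0.25:

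- site level: a = 0.3875, d = 0.425, p_o = 0.8125, p_e = 0.50, kappa = 0.625;
- patient level: a = 0.3875, d = 0.30, p_o = 0.6875, p_e = 0.50, kappa = 0.375.

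| f | Kappa, site-level knowledge | Kappa, patient-level knowledge |
|---|---|---|
| 0 | 0.50 | 0.50 |
| 0.10 | 0.55 | 0.45 |
| 0.25 | 0.625 | 0.375 |
| 0.50 | 0.75 | 0.25 |

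The same calculation was run over q = 0.3, 0.5, 0.7 and s/c = 0.7/0.8, 0.8/0.8, 0.6/0.9. At f = 0.25, site-level knowledge raises kappa by about 0.10 to 0.13 and raw agreement by 5 to 8 percentage points. Patient-level knowledge lowers kappa in all nine combinations, by about 0.07 to 0.19. On the section 6.4 bands, 0.50 is moderate, 0.625 good and 0.375 fair.

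**5. A binary patient-level comparison.** At 20% positivity, 0.20 × 30 = 6 patients would be rated, all PET-positive. If m of the 6 are MRI/CT-positive, p_o = m/6 and p_e = m/6. Kappa is then 0 for m = 3, 4 or 5 and undefined for m = 6. Raw agreement rises with each extra positive MRI/CT call, but kappa does not. This comes from the restriction to PET-positive patients, a separate weakness that the same fix addresses.

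**The case against.** The sponsor has several fair replies.

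- *The word first is honoured.* It means before the fused read, and that order is kept. This stands: the plan lacks a safeguard, but it does not contradict itself.
- *Separate readers are possible.* Two specialties are named, and a molecular imager could read the PET while an abdominal imager rates the MRI/CT. This stands as a possibility. It would remove site-level knowledge, but not the knowledge that every rated case is PET-positive.
- *The restriction may define an analysis set and not a reading sequence.* This is possible, but the instruction that the PET call is made initially weakens it.
- *Intrahepatic disease is already established.* Section 3.3 requires viable HCC of at least 1.5 cm on standard-of-care imaging, and section 3.1 places the scan within 4 weeks of that imaging. This limits how far PET can shift the score for the qualifying lesion. It does not cover additional lesions or extrahepatic disease, which are also rated.
- *Concordance does not drive the decision.* The hypothesis, the interval calculations and the 20% criterion all concern SSTR positivity, and section 6.4 calls the work largely exploratory and descriptive. This stands and limits the severity, although section 5.1 does list concordance under Primary Endpoint.

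**Conclusion.** The point holds as a missing safeguard, and it should be fixed. Under sections 4.6.4 and 6.4 the MRI/CT-alone rating is made after, and only because of, a positive PET read, with no masking specified. Concordance is open to review bias: most likely towards agreement if PET findings are known site by site, and of uncertain direction for kappa otherwise. The size cannot be derived from the documents. The kappa shifts shown rest entirely on assumed accuracy, prevalence and pull.

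A reader might infer more, and the documents do not support it:

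- That the anatomic rater has certainly seen the PET images. The plan does not say who performs which step; only knowledge of patient-level PET status follows, and only for a rater who knows how cases are selected.
- That kappa will be inflated. This needs site-level knowledge. With patient-level knowledge alone, kappa fell in every combination tried.
- That the damage is permanent. Section 4.6.4 has the images anonymised and stored, so a new, masked reader could rate them again.
- That the main result is compromised. The SSTR-positivity estimate comes from the PET call, which does not depend on the anatomic 1-5 score, so neither it nor the 20% go decision is affected.

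**What to change.** Reword sections 4.6.4 and 6.4 so that, for every scanned patient:

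1. intrahepatic and extrahepatic disease is rated 1-5 on the anatomic images with PET hidden, and the score is locked;
2. the PET is then opened, and the positive/negative call and binding grade are made;
3. the fused images are rated 1-5.

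Remove the step that selects patients for the MRI/CT-alone rating by their PET result. This order protects the anatomic score whether one reader or several are used, and whichever way the bias would have run.

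The change needs no additional scans or readers. The cost is the rewording and the recording of anatomic ratings for PET-negative patients as well, at most 30 patients in total. If any reads have already been done in the present order, the stored anatomic images can be re-rated by a reader masked to PET result and to case selection.
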